8.3 Study procedure

Of patients still alive who want to participate in the follow-up study and patients who have died, the medical record and any available radiological imaging are reviewed retrospectively by members of the study team.

All patients who are still alive and want to participate in this study will be asked to visit the hospital once for physical examination and an ultrasound of the abdominal wall. Subsequently, all those patients will be asked to complete five validated questionnaires related to quality of life, cosmesis, body image and abdominal wall function. There is no set time after randomization in the original STITCH trial when the questionnaires should be completed. Indeed, this would mean that data collection would have to spread out over a few years which is not desirable.

After the physical examination and ultrasound are performed, the patient is given a brief explanation of the five questionnaires to be completed. The patient can choose whether to complete these questionnaires digitally at home or on paper at home (and return them free of charge).

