Main study parameters/endpoints: The primary outcome measure is the 10-year midline incisional hernia rate. The primary endpoint will be determined for the 545 patients of the original intention-to-treat population using Kaplan Meier analysis. In patients who died during follow-up, this will be evaluated by reviewing the available medical charts and radiological studies. CT-scans of the abdomen will be evaluated by the study-team. If CT imaging is not available, documented findings during physical examination by the relevant medical specialist will be considered. Patients being still alive with written informed consent to be contacted will be approached for their willingness to participate in this follow-up study, and after consent, we will reassess CT scans for an incisional hernia. All patients who are still alive and want to participate in this study will be asked to visit the hospital once for physical examination and an ultrasound of the abdominal wall. Secondary outcome parameters include QoL and cosmetic outcome, Patients still alive with consent for participation will be sent the following questionnaires: MOS SF-36 and EQ-5D (QoL), Dresden Body Image Questionnaire (body image), Body Image Questionnaire (cosmesis), Hernia-Related Quality of Life Survey (abdominal wall function). Furthermore, readmission and surgical intervention rates related to midline IH will be determined for the entire study population.

Nature and extent of the burden and risks associated with participation, benefit and group

relatedness: Undergoing an ultrasound, physical examination and completing several questionnaires may be considered burdensome for the patient.

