4.2 Inclusion criteria

In order to be eligible to participate in this study, a subject must meet the following criteria:

- Available signed informed consent form for the original STITCH trial of the patients who are still alive. Of the patients who have died, the medical records are reviewed.
- Patients must give informed consent for the current study, the long-term follow-up of the STITCH trial.

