11.2 Recruitment and consent

Patients who were included in the original STITCH trial and who are still alive will be approached by the study coordinator or the surgeon from the hospital they were included at the time, for participation in the follow-up study. Patients will only be approached if they have not checked the box on the Informed Consent Form of the original STITCH trial that they do not wish to be approached in the future for follow-up studies. Patients who indicated they had no objection to being approached will be contacted by telephone for participation and explanation of the study. If the patient approves, we will then send a subject information sheet with an informed consent form that allows the patient to make a well-informed and well-considered decision whether or not to participate in this follow-up study. The informed consent form can be returned free of charge by the patient when participation.

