11.4 Benefits and risks assessment, group relatedness

Undergoing an ultrasound, physical examination and completing several questionnaires may be considered burdensome for the patient.

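### Late record and CT review of living patients depends on one decision to participate, and the visible protocol offers no records-only consent to those put off by the visit or questionnaires

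*Protocol*

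**What the plan says.** Section 8.3 sets the scope of the retrospective review: "Of patients still alive who want to participate in the follow-up study and patients who have died, the medical record and any available radiological imaging". The study team examines these sources. Death therefore brings a patient into the review without further steps, while a living patient must first want to take part. The Summary (main study parameters) has the same order for living patients: they are approached, "and after consent, we will reassess CT scans for an incisional hernia". Section 4.2 makes this an inclusion criterion: "Patients must give informed consent for the current study, the long-term follow-up of the STITCH trial".

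Section 11.2 describes the approach. Patients who did not object to later contact are telephoned. If they approve, "we will then send a subject information sheet with an informed consent form". One decision, to participate or not, is described.

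Section 8.3 then says what participants are asked to do: "All patients who are still alive and want to participate in this study will be asked to visit the hospital once". The visit consists of a physical examination and an ultrasound. The section then adds a further request to the same group: "Subsequently, all those patients will be asked to complete five validated questionnaires". Section 11.4 acknowledges the load: "Undergoing an ultrasound, physical examination and completing several questionnaires may be considered burdensome for the patient".

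On scope, the Summary (study design) announces a review of files and imaging for the whole trial cohort, and section 10.1 analyses the primary outcome in 545 patients by intention to treat. For patients who died, section 8.1.1 takes charts and radiology as the source of the primary endpoint, with documented physical examination where there is no CT.

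**The concern.** The information that can settle the primary endpoint in a patient who died also exists, at least in part, for a living patient who cannot or will not travel. The visible text gives that patient no way to allow its use without agreeing to take part in the study as a whole. Someone who hears on the telephone about a visit, an ultrasound and five questionnaires and says no falls outside the review in section 8.3, even if they would have allowed their file to be read.

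The burden of the added procedures, and not an objection to sharing data, may then decide who has late primary-endpoint data. Willingness to attend an abdominal wall check could plausibly depend on mobility or abdominal complaints, although the protocol gives no data on this. Analysis cannot recover what was not collected. Such patients could only be censored at their original follow-up or have their status estimated by the regression model of section 10.1.

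**Working it through.** No figure in the plan depends on this point, so the main check is to follow each type of patient through the text.

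| Patient | Late record and CT review described? | Source |
|---|---|---|
| Died during follow-up | Yes | 4.2, 8.1.1, 8.3 |
| Alive, consents, attends the visit | Yes | 8.3, Summary |
| Alive, consents, does not attend | Not excluded: review is tied to participation and consent, not attendance. Not stated explicitly either | 4.2, 8.3 |
| Alive, refuses on the telephone | No: no form is sent and the consent criterion is not met | 4.2, 8.3, 11.2 |
| Alive, opted out of later contact in the original trial | No: excluded by criterion and not approached | 4.3, 11.2 |

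The fourth row is the gap. The fifth follows from an earlier choice by the patient, and the change proposed here does not affect it.

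**Scope.** The arms sum to the stated total: 268 + 277 = 545. Section 10.1 analyses all 545 and the Summary promises file review for the whole cohort, but patients in the fourth row cannot be reviewed under section 8.3. They still have their data from the original trial.

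**Size.** The protocol gives neither the share alive nor the expected refusal rate, so both are assumptions:

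patients without late review = 545 × share alive × share of the living who decline

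- Low: 545 × 0.40 × 0.20 = 43.6, about 44 (44/545 = 8%).
- High: 545 × 0.60 × 0.40 = 130.8, about 131 (131/545 = 24%).

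Wider assumptions (30 to 70% alive, 10 to 50% declining) give:

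- Low: 545 × 0.30 × 0.10 = 16.35, about 16 (3%).
- Middle, at 50% alive and 30% declining: 545 × 0.50 × 0.30 = 81.75, about 82 (15%).
- High: 545 × 0.70 × 0.50 = 190.75, about 191 (35%).

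These count all living decliners. How many decline because of the visit or questionnaires, and how many of those would accept review of records alone, cannot be derived from the protocol.

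**The case against.** A reader might infer that a patient who declines the visit thereby loses record and CT review. The text does not support that. Participants are asked to attend, no passage makes attendance a condition, and the exclusion criteria in section 4.3 do not mention non-attendance. A patient who consents and stays at home is not said to lose anything. This part of the objection stands, and the point is confined to patients who refuse participation as a whole.

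The consent form and the flowchart of the approach to patients are not visible, so a tiered form may exist. That also stands, but it does not close the gap. Under section 11.2 the form goes only to those who have agreed by telephone, so a patient who refuses on the call never sees its options.

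The protocol already limits the burden: there is one visit, questionnaires are completed at home digitally or on paper, and travel costs can be reimbursed (8.3, 11.6). These measures reduce refusals but give those who still refuse no alternative.

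A reader might also infer a biased comparison between small and large bites. Nothing in the protocol shows that refusal would differ by arm, and the original trial was double-blind. That reading is not supported.

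Finally, a lighter option could draw some willing patients away from active examination. This is a real trade-off, and it is why the full request should come first.

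**Conclusion.** The point holds in its limited form. For living patients, late review for the primary endpoint rests on a single decision to participate. The visible text has no records-only alternative, and a refusal on the telephone ends the matter. This works against the protocol's own aim of reviewing the whole cohort and analysing 545, and it leaves unused a source that the protocol accepts for patients who died.

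The size is unknown. The range of about 44 to 131 of 545 (8 to 24%) rests wholly on the assumed shares alive and declining. The consequence is lost precision and, if refusal is related to hernia status, a distorted absolute 10-year rate. The change is worth making because it is cheap and concerns the primary endpoint. The conclusion rests on sections 4.2, 8.3 and 11.2 and the Summary, and would weaken if the telephone approach, which is described only briefly, already includes a records-only fallback.

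**What to change.** Amend sections 4.2, 8.3 and 11.2 and the telephone script as follows:

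- Ask every eligible living patient for full participation first.
- Offer those who decline the visit or the questionnaires consent to review of the medical record and existing imaging alone, and send them a form for this.
- State that a participant who does not attend the visit still has records and CTs reviewed.
- Include all of these patients in the primary analysis, and report by arm how many are at each level of participation.
- If the consent form already has such levels, bring these sections and the telephone approach into line with it.

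The cost is rewording of the protocol, form and script. The downside is that a few patients who would have attended may choose the lighter option, so that their hernia status rests on records alone, as it already does for patients who died. Asking for full participation first limits this.

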8.2 Randomisation, blinding and treatment allocation

Not applicable as no additional randomisation or blinding will be performed in this study. Patients had already been randomized at the time they were included in the original RCT.

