10.2 Secondary study parameter(s)

Statistical comparison of quality of life, body image, cosmetic results and abdominal wall function between patient groups (small vs large bites technique and with or without incisional hernia) will be done by multilevel analysis (linear mixed-effects model with random effect for each patient) (7).

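### The questionnaires are completed after the examination and ultrasound, so a newly learned hernia finding can influence answers that are then compared by hernia status

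*Protocol*

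**What the plan says.** Section 8.3 asks every living participant to "visit the hospital once for physical examination and an ultrasound of the abdominal wall". The questionnaires follow: "Subsequently, all those patients will be asked to complete five validated questionnaires related to quality of life, cosmesis, body image and abdominal wall function". The same section then repeats the order: "After the physical examination and ultrasound are performed, the patient is given a brief explanation of the five questionnaires to be completed". Completion is away from the clinic: "The patient can choose whether to complete these questionnaires digitally at home or on paper at home (and return them free of charge").

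Section 8.1.2 makes all the secondary outcomes self-reported: SF-36, EQ-5D, two body-image instruments and the hernia-specific HerQLes survey. Section 10.2 compares them in two ways: "small vs large bites technique and with or without incisional hernia". Section 8.2 states that "no additional randomisation or blinding will be performed in this study". The Summary says only that "Patients still alive with consent for participation will be sent the following questionnaires", with no timing relative to the visit.

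**The concern.** Answers about body image, abdominal wall burden and general health are subjective. A patient who has just been scanned for a hernia may know the result when filling in the forms. Someone with a symptom-free gap first seen on ultrasound may report a worse abdominal wall than the day before; someone found to be clear may report a better one. Both movements widen the difference between patients with and without hernia, which is also the direction the Introduction leads one to expect, since it describes hernia as capable of harming body image and quality of life.

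At stake is the interpretation of one planned secondary comparison. A difference by hernia status would be read as the burden of having a hernia, when part of it could be the effect of having recently been told about one.

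**Working it through.** No figure in the protocol can be reproduced here, so the check is to read the sections together.

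1. **Order.** Section 8.3 gives it twice, and both statements agree: visit, examination and ultrasound, then explanation, then completion at home. No other section provides for completion before the visit. The Summary is silent on order, so it neither contradicts section 8.3 nor softens it.

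2. **Access to the finding.** No section withholds the result until the forms are returned, and section 8.2 adds no blinding. No section says that the result is disclosed either. What is established is opportunity; disclosure at an in-person examination is likely but not stated.

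3. **Link to the grouping.** The Summary describes the visit under the main study parameters, so its findings bear on hernia status. The Introduction's definition covers a gap with or without a bulge, found clinically or on imaging. A patient with no prior awareness of a hernia can therefore enter the hernia group because of the visit ultrasound.

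4. **Who is exposed.** Patients whose hernia was already known, symptomatic or repaired would know their status under any order. Exposure is confined to hernias first found at the visit and to patients reassured that they have none.

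5. **Form of the bias.** Let p be the share of the hernia group first detected at the visit, d the worsening in score caused by learning of it, and r the average improvement in the no-hernia group from reassurance. The hernia contrast is then widened by p × d + r. The protocol gives none of p, d or r.

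6. **Comparison of trial arms.** Here the finding acts only through a difference between arms in the share of patients who receive each kind of news. If the share of newly found hernias differed by 5 percentage points and d were 0.5 SD (both assumptions), the shift would be 0.05 × 0.5 = 0.025 SD. The hernia contrast takes the effect directly; the arm contrast takes only its imbalance.

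7. **Can analysis remove it?** Section 2 collects presence, duration, recurrence and repair of hernias, and section 8.3 reviews records and imaging. Previously documented hernias can thus largely be separated from newly found ones. Restricting the hernia group to the former removes the p × d term but leaves r. It also changes the question, because newly found hernias are likely to be the less symptomatic ones, so what is dropped is not only the disclosure effect.

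**The case against.** The strongest reply is that disclosure is inferred. A reader might take the protocol to say that patients answer having been told the result; it does not, and only the opportunity is documented. That limits the point to what can happen, but it does not remove it.

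A reader might also attach a size. Assuming p of 15–40%, d of 0.2–0.5 SD and r of 0–0.1 SD gives 0.15 × 0.2 + 0 = 0.03 SD up to 0.40 × 0.5 + 0.1 = 0.30 SD. Every input is invented, and the upper end stacks three extremes. The Introduction also says that most incisional hernias become apparent and symptomatic within five years, while follow-up here is 10–13 years, so many affected patients may already know. The range is not evidence of a bias of that size.

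It is tempting to say that the bias cannot be dealt with in analysis. The hernia history and record review allow a partial separation, so that goes too far.

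A further inference would be that the forms depend on attending, so that consenting patients too frail to travel are lost. The documents do not support this. The Summary sends the forms to living, consenting patients, section 8.1.2 reports these outcomes from all of them, and section 8.3 nowhere makes attendance a condition.

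Finally, the present order has a plausible purpose. Two of the five instruments were translated from English, with Dutch validation reported only for the other three, and the explanation at the visit may help patients complete them. Moving the forms is therefore not free. This objection stands as a cost, but the explanation can be given at another point.

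**Conclusion.** The point holds in a limited form. Section 8.3 fixes an order that allows the examination and ultrasound finding to reach the patient before the self-report, and section 10.2 compares that self-report by hernia status. The exposed part is hernias first detected at the visit and patients reassured of having none.

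The conclusion assumes that at least some patients learn the result before completing the forms and that the knowledge affects some answers. The size of the effect cannot be estimated from the documents. The primary 10-year hernia rate does not use the questionnaires and is unaffected. The randomised comparison of small and large bites is little affected. The exposed contrast is secondary and non-randomised, so this is an inexpensive improvement to data collection and not a threat to the trial's main conclusion.

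**What to change.** Amend section 8.3 so that the five questionnaires are sent once the signed consent form is returned and are completed before the physical examination and ultrasound, or on arrival if not yet done. Record the completion date relative to the visit, so that forms completed afterwards can be identified. State the same order in the Summary.

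Section 11.2 already provides for a telephone call and a mailed information sheet and consent form, and section 8.3 ties the questionnaires to no set time since randomisation, so earlier completion conflicts with nothing in the schedule. The cost is a changed mailing step and a new place for the brief explanation: with the mailing, in the telephone call, or on arrival. Patients who arrive without completed forms would fill them in at the hospital. By the item counts in section 8.1.2 that is 36 + 14 + 35 + 10 + 12 = 107 items, and those patients would lose the choice of completing them at home.

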8.4 Withdrawal of individual subjects

Subjects can leave the study at any time for any reason if they wish to do so without any consequences.

8.4.1 Specific criteria for withdrawal

Patients can withdraw their consent at any time during the study without having to give reason.

8.5 Replacement of individual subjects after withdrawal

Not applicable, all patients are already asked to participate so substitution is not possible when they withdraw their informed consent.

8.6 Follow-up of subjects withdrawn from treatment

Not applicable as patients do not receive treatment.

8.7 Premature termination of the study

Not applicable, the study will not be terminated prematurely.

9. SAFETY REPORTING

9.1 Temporary halt for reasons of subject safety

In accordance to section 10, subsection 4, of the WMO, the sponsor will suspend the study if there is sufficient ground that continuation of the study will jeopardise subject health or safety. The sponsor will notify the accredited METC without undue delay of a temporary halt including the reason for such an action. The study will be suspended pending a further positive decision by the accredited METC. The investigator will take care that all subjects are kept informed.

9.2 AEs, SAEs and SUSARs

9.2.1 Adverse events (AEs)

Not applicable, as this study does not involve an investigational medical product and this study is not subject to WMO.

9.2.2 Serious adverse events (SAEs)

Not applicable, as this study does not involve an investigational medical product.

9.2.3 Suspected unexpected serious adverse reactions (SUSARs)

Not applicable, as this study does not involve an investigational medical product.

9.3 Annual safety report

Not applicable, as this study does not involve an investigational medical product.

9.4 Follow-up of adverse events

Not applicable, as this study does not involve an investigational medical product.

9.5 Data Safety Monitoring Board (DSMB) / Safety Committee

Not applicable, since this follow-up study has a retrospective character.

10. STATISTICAL ANALYSIS

10.1 Primary study parameter(s)

We will analyse the primary outcome for the 545 patients using Kaplan Meier analysis and log-rank test to compare the two trial groups based on an intention-to-treat basis (7). Statistical analyses will be performed using IBM® SPSS® Statistics Version 29. In the case of missing data, a regression model is used to estimate the missing values.

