2. OBJECTIVES

Primary Objective:

The primary objective of the original STITCH trial was reduction of the incidence of an incisional hernia after open, elective abdominal surgery. The primary objective of the present study is to determine the difference in incidence of incisional hernia between the intervention group and the control group of the original STITCH trial after 10 years of follow-up from the time of randomization,.

Secondary Objectives:

The secondary objectives of this follow-up study are to measure quality of life (QoL), body image and cosmetic results and abdominal wall function in those patients who are still alive.

[figure not shown]
In addition, all information is collected regarding the abdominal wall hernia (presence, location, duration, size, recurrence, repair) and other abdominal wall related complications such as: open abdomen, enterocutaneous fistula, wound problems, burst abdomen, number of abdominal reoperations, number of hospital admissions (and total days) with/without development of ileus.

STUDY DESIGN

The original STITCH trial (NCT01132209) was a multicenter double-blind prospective randomized controlled trial who randomly assigned 560 patients between October 2009 and March 2012 in the intervention group (small bites) or in the control group (large bites). Ultimately, 268 patients were included in the intervention group and 277 patients in the control group. A total of 545 patients.

This current study is a long-term (10-13 years) follow-up of the original STITCH trial.

The flowchart below graphically depicts the process of approaching the patients who were included in the original STITCH trial. On the original informed consent form of the STITCH trial patients were asked if they agreed to being contacted for a follow-up study after completion the original trial.

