8. METHODS

8.1 Study parameters/endpoints

8.1.1 Main study parameter/endpoint

The primary outcome measure is the 10-year midline incisional hernia rate. The size (diameter) and location of the hernia will be documented.

In patients who died during follow-up, this will be evaluated by reviewing the available medical charts and radiological studies. CT-scans of the abdomen will be evaluated by the study-team. If CT imaging is not available, documented findings during physical examination by the relevant medical specialist will be considered. The CT scans of patients being still alive will be reassessed for an incisional hernia.

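### The 10-year hernia rate is fixed as a Kaplan-Meier estimate with no competing event for death, so the estimator overstates the share of patients who develop a hernia

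*Protocol*

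**What the plan says.** Section 8.1.1 defines the endpoint: "The primary outcome measure is the 10-year midline incisional hernia rate". The primary objective in section 2 reads: "determine the difference in incidence of incisional hernia between the intervention group and the control group of the original STITCH trial after 10 years".

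The estimator is named twice. The Summary says "The primary endpoint will be determined for the 545 patients of the original intention-to-treat population using Kaplan Meier analysis", and section 10.1 says "We will analyse the primary outcome for the 545 patients using Kaplan Meier analysis and log-rank test to compare the two trial groups".

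Deaths are foreseen. The study design text says "This current study is a long-term (10-13 years) follow-up of the original STITCH trial". Section 8.1.1 gives the deceased their own route of assessment: "In patients who died during follow-up, this will be evaluated by reviewing the available medical charts and radiological studies". Survivors who take part are also examined (section 8.3): "All patients who are still alive and want to participate in this study will be asked to visit the hospital once for physical examination", together with an ultrasound.

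No section names death as a competing event, mentions a cumulative incidence function, or says that the target is the risk in the absence of death. The regression rule for missing data in section 10.1 does not mention death, and a death is not a missing value. The protocol does not write out that hernia-free deaths are censored. That is the ordinary meaning of a Kaplan-Meier analysis, and no other rule is given.

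**The concern.** Censoring a patient at death treats that patient as still able to develop a hernia later, at the same rate as those who remain under observation. 1-KM at 10 years is then a risk in a hypothetical population in which nobody dies. The protocol's wording (rate, incidence) points to something else: the proportion of randomised patients who develop a hernia by year 10. As an estimator, 1-KM can never be below that proportion, and it is above it as soon as some hernia-free deaths precede later hernias. The Introduction places most hernias within the first five years, so hernias after year 1 are to be expected.

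The per-arm 10-year rates are the declared primary outcome and will be read as the share of patients who got a hernia. The concern is with these absolute rates and, to a smaller degree, with the absolute difference. It does not extend to the log-rank test, which remains a valid comparison of cause-specific hernia hazards if censoring is otherwise non-informative.

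**Working it through.** The protocol states no 10-year rate, mortality, event count or power, so there is no planned figure to reproduce. The group sizes agree with the total: "268 patients were included in the intervention group and 277 patients in the control group", and 268 + 277 = 545.

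**Inputs from the protocol.** One-year hernia risks of 21% (large bites) and 13% (small bites), from the Introduction, and the group sizes above.

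**Assumed inputs.** Constant hernia hazard after year 1 of h = 0.01, 0.02, 0.03 or 0.04 per year. For small bites this is either the same h or 0.6h; the year-1 hazard ratio is ln(0.87)/ln(0.79) = 0.59. Ten-year mortality M = 30, 40, 50 or 60%, the same in both arms and independent of hernia. This gives 16 combinations per scenario.

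**Formulas.**
- Year-1 hernia hazard: h1 = -ln(1 - 0.21) = 0.2357 for large bites and -ln(1 - 0.13) = 0.1393 for small bites.
- Death hazard: m = -ln(1 - M)/10.
- 1-KM at 10 years = 1 - exp(-(h1 + 9h)).
- Cumulative incidence (CIF) = h1/(h1+m) × (1 - exp(-(h1+m))) + exp(-(h1+m)) × h/(h+m) × (1 - exp(-9(h+m))).

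**One case in full** (large bites, h = 0.03, M = 50%, so m = 0.0693):
- 1-KM = 1 - exp(-(0.2357 + 0.27)) = 39.7%.
- CIF = 0.2032 + 0.7371 × 0.3021 × 0.5909 = 0.2032 + 0.1316 = 33.5%.
- Excess = 6.2 points. The arm's 95% half-width is 1.96 × sqrt(0.335 × 0.665/277) = 5.6 points.

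**Large bites, all 16 cases** (CIF in %, excess of 1-KM in points in brackets, rounded separately; * marks an excess larger than the arm's half-width, which is about 5.1 to 5.8 points):

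| h per year | 1-KM | M = 30% | M = 40% | M = 50% | M = 60% |
|---|---|---|---|---|---|
| 0.01 | 27.8 | 26.3 (1.5) | 25.7 (2.1) | 25.1 (2.7) | 24.4 (3.4) |
| 0.02 | 34.0 | 31.4 (2.6) | 30.5 (3.5) | 29.4 (4.6) | 28.3 (5.7)* |
| 0.03 | 39.7 | 36.2 (3.5) | 34.9 (4.8) | 33.5 (6.2)* | 31.9 (7.8)* |
| 0.04 | 44.9 | 40.5 (4.3) | 38.9 (5.9)* | 37.2 (7.7)* | 35.3 (9.6)* |

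For small bites the excess is 1.5 to 10.1 points with equal late hazards, and 1.0 to 6.8 points with a late hazard ratio of 0.6.

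**Simulation check.** With 200,000 simulated large-bites patients at h = 0.04 and M = 50%, 1-KM was 44.9% and the share who actually developed a hernia was 37.2%, as in the table.

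**Difference between arms.**
- Equal late hazards: the 1-KM difference runs from 0.55 points too small (5.58 against 6.13; h = 0.04, M = 60%) to 0.07 too large (7.31 against 7.24; h = 0.01, M = 60%). It is too small in 12 of 16 cases.
- Late hazard ratio 0.6: it is too large by 0.5 points (10.2 against 9.7) to 2.8 points (15.0 against 12.2).
- For scale, the 95% half-width of a risk difference with risks near 30% is 1.96 × sqrt(0.21/277 + 0.21/268) = 7.7 points.

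**Log-rank test.** With equal hernia hazards, 277 and 268 patients and 4,000 runs, the simulated type I error was 4.6% with 50% mortality in both arms and 4.8% with 50% against 65%.

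**The case against.** **The censoring rule is inferred, and the analysis plan is not shown.** True, but the protocol itself names the estimator twice. A plan consistent with it inherits Kaplan-Meier, so this is a point about what is fixed and not about missing detail.

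**The risk in the absence of death is a recognised target for the durability of a closure technique, and it does not depend on the cohort's mortality.** That is fair. It would justify a clearly labelled 1-KM as a secondary figure. The protocol does not declare that target, however, and its wording will be read as the share of patients affected.

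**The objective is comparative, and the comparison is barely touched.** This stands. The error in the difference lies inside sampling error in every case examined, and the test is sound. The difference is overstated only if the small-bites benefit continues after year 1, which the protocol does not establish.

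**The size is assumed, and a constant late hazard favours the concern.** This stands in part. If each case keeps its total late hazard but 80% of it falls in years 1 to 5, the large-bites excess becomes 1.2 to 7.5 points and is larger than the half-width in 3 of 16 cases instead of 6. With 4% per year in years 2-5 and 1% in years 6-10, it is 2.3 points (36.0% against 33.7%, 30% mortality) to 5.2 points (36.0% against 30.7%, 60% mortality). In the main grid, an excess above sampling error needs at least 40% mortality and a late hazard of at least 2% per year.

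**Hernias missed in the deceased, who have only charts and existing imaging, may push the observed rate down.** This also stands. It is a separate bias, and the net error of the published rate is not claimed here.

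**Conclusion.** The concern holds. With hernia-free deaths censored, the named estimator gives per-arm 10-year rates at or above the proportion of patients who develop a hernia. The direction is mathematical. The size depends on mortality and late hernia rates that the protocol does not give. Under the assumed ranges it is 1.5 to 9.6 points for large bites, which can exceed that arm's sampling error but does so only in the less favourable scenarios. The arm difference moves by at most 0.55 points with equal late hazards and 2.8 points with a late hazard ratio of 0.6, and the log-rank comparison is unaffected. This should be fixed: the headline rates are mis-estimated in a known direction, while the between-arm conclusion largely survives.

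**What to change.** In the Summary and sections 8.1.1 and 10.1, define the 10-year rate in each arm as the Aalen-Johansen cumulative incidence, with death without hernia as a competing event. Report the 10-year risk difference with its 95% confidence interval, and show deaths by arm beside it. Keep the log-rank test and label it a comparison of cause-specific hernia hazards; Gray's test is optional. Do not present 1-KM as the 10-year rate. If it is wanted at all, give it as a labelled secondary figure for the risk in the absence of death.

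The cost is wording in three places and a cumulative-incidence routine. Section 10.1 fixes SPSS version 29, so that sentence should allow whatever software the routine needs. No new visit is required. Date of death must be taken from the records under review; the protocol does not list it as collected, but censoring at death needs it in any case. The reported rates will be somewhat lower and will depend on this cohort's mortality, which is why deaths by arm must accompany them.
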